## 10 Safety Analyses

*When calculating the incidence of adverse events, or any sub-classification thereof by treatment, time period, severity, etc., each subject will only be counted once and any repetitions will be ignored; the denominator will be the total population size.*

Per ClinicalTrial.gov reporting requirements, three tables summarizing adverse events are required and will be created:

- All-Cause Mortality (only required if primary outcome completion date is on or after 01/18/2017): A table of all anticipated and unanticipated deaths due to any cause, with number and frequency of such events in each arm/group of the clinical study.
- Serious Adverse Events: A table of all anticipated and unanticipated serious adverse events, grouped by organ system, with number and frequency of such events in each arm/group of the clinical study. (See Adverse Events definition below).

- Other (Not Including Serious) Adverse Events: A table of anticipated and unanticipated events (not included in the serious adverse event table) that exceed a frequency threshold (for example, 5 %) within any arm of the clinical study, grouped by organ system, with number and frequency of such events in each arm/group of the clinical study.

## 10.1 Adverse Events

When calculating the incidence of adverse events, or any sub-classification thereof by treatment, time period, severity, etc., each subject will only be counted once and any repetitions of adverse events will be ignored; the denominator will be the total population size. The summary statistics will be produced in accordance with section 9.

## 10.2 Pregnancies

The study did not perform any pregnancy tests as trying to conceive was an exclusion factor.

## 11 Reporting Conventions

P-values  $\geq 0.001$  will be reported to 3 decimal places; p-values less than 0.001 will be reported as " $<0.001$ ". The mean, standard deviation, quantiles, and any other statistics will be reported to two decimals. Estimated parameters will be reported to 2 significant figures.

## 12 Quality Assurance of Statistical Programming

Final statistical analysis will be performed using R on an Oregon Health and Sciences encrypted computer with Windows operating system that is stored in a locked office. R packages to be utilized will include lme4, lmerTest, emmeans, Rmisc, and rstatix for statistical analyses; tidyverse, GGally, ggpubr for data visualization; table1, crosstable, flextable, sjPlot, and stargazer for table creation.

To provide high quality code that is understandable, and allows reproduction of the analysis the following points will be followed: At the start of any code file there will be a set of comments that give: the author; the date and time of writing; references to inputs and outputs; reference to any parent code file that runs the child code file.

## 13 Summary of Changes to the Protocol and/or SAP

04/08/2024 updates to the SAP were made to include the analysis plan for Protocol 2 and the Exploratory ANCOVA analysis plan to include corrected definition of acute reductions of post-session supine blood pressure.

04/11/2024 updates to the SAP were made to 1) utilize the memory and list-sorting age-corrected scores rather than percentiles to calculate the Project 2 Aim1 primary outcome composite cognitive score due to their more normal distributions and 2) update the primary efficacy analysis model from mixed effect model to robust linear regression with Huber weighting. Due to there being no interim data collection timepoint for cognitive and MRI measures, pre-intervention values can be included as covariate rather than the more complex approach of including a time x group interaction. Assessment of residual plots indicated potential influential outliers, the impact of which can be mitigated through use of a

robust regression approach.

05/22/24 The SAP was updated to include correlations between pre- to post-intervention in ambulatory and in clinic systolic and diastolic pressure and change from pre- to post first intervention session supine systolic and diastolic blood pressure.

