## 4 Study Objectives and Endpoints

### 4.1 Study Objectives

#### Protocol 1

**Specific Aim 1:** Utilizing a prospective randomized clinical trial study design, we will determine whether heat therapy improves **blood pressure** (both in clinic and ambulatory) better than dynamic aerobic exercise, the gold-standard non-pharmacological treatment of essential HTN. Specifically, we hypothesize that 30 sessions of passive heat therapy using hot water immersion over 8-10 weeks will improve blood pressure in HTN individuals to a greater extent than 30 sessions of exercise training over the same time period.

**Specific Aim 2:** We will determine whether heat therapy will improve biomarkers of arterial health and compare responses to exercise training. We hypothesize that 30 sessions of heat therapy will improve arterial stiffness in HTN to a greater extent than exercise. Furthermore, we hypothesize key clinical biomarkers of systemic inflammation and oxidative stress will be improved following heat therapy.

**Specific Aim 3:** In an exploratory aim, we will determine whether the acute decreases in blood pressure following an initial heat therapy session or exercise peak test predict the sustained reduction in resting blood pressures following heat therapy treatment or exercise training in HTN. These findings would provide significant predictive information beyond baseline resting blood pressures. We hypothesize that the reduction in blood pressure following acute stressors will be predictive of treatment effects on resting blood pressure.

#### Protocol 2

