**HEAT THERAPY VS EXERCISE TRAINING IN HYPERTENSION SAP**

dbp_dipper	Aim 1/Secondary	Categorical; non-dipper <10%, dipper ≥10% to <20%, and extreme dipper ≥20% change in diastolic BP at night calculated from ambulatory BP day and night averages
pwv	Aim 2/Primary	Continuous; average of three pulse wave velocity measurements collected at pre-, interim-, and post-intervention timepoints
il6_lg2	Aim 2/Secondary	Continuous; Biomarker IL-6 with the lower limit of detection (LLD) of 0.031 imputed for <LLD, log2 transformed for normalcy
crp_lg2	Aim 2/Secondary	Continuous; Biomarker CRP with the lower limit of detection (LLD) of 0.031 and upper LD (ULD) of 50 imputed for <LLD and >ULD, log2 transformed for normalcy
et1_lg2	Aim 2/Secondary	Continuous; Biomarker ET-1 with the lower limit of detection (LLD) of 0.031 imputed for <LLD, log2 transformed for normalcy
alb_lg2	Aim 2/Secondary	Continuous; Biomarker urine albumin with the lower limit of detection (LLD) of 0.031 imputed for <LLD, log2 transformed for normalcy
Supine.SBP.low	Aim 3/Primary	Continuous; average of three lowest consecutive supine systolic blood pressure measurements taken every 5 minutes for an hour post-intervention during supine recovery (for Heat Therapy: syst_bp55_ht_s1 to syst_bp110_ht_s1; for Exercise Training: for Heat Therapy: syst_bp55_ex_s1 to syst_bp110_ex_s1)
Supine.DBP.low	Aim 3/Primary	Continuous; average of three lowest consecutive supine systolic blood pressure measurements taken every 5 minutes for an hour post-intervention during supine recovery (for Heat Therapy: syst_bp55_ht_s1 to syst_bp110_ht_s1; for Exercise Training: for Heat Therapy: diast_bp55_ex_s1 to diast_bp110_ex_s1)
Supine.SBP.1.ch	Aim 3/Primary	Change from average pre-session resting SBP to Supine.SBP.low
Supine.DBP.1.ch	Aim 3/Primary	Change from average pre-session resting DBP to Supine.SBP.low
eGFR	Aim 1/Exploratory	eGFR was calculated using the CKD-EPI Creatinine-Cystatin Equation (2021) using the CKDEpi_RF.creat.cys function in the nephron R package and rounded to two decimal places
uacr	Aim 1/Exploratory	Urine albumin creatinine ratio (mg/g) was calculated by dividing urine albumin by urine creatinine/1000 rounded to 2 decimal places
Protocol 2		
cognitive_score	cognitive/Primary	Averaged z-scores (centered & divided by standard deviation) of age-corrected picture sequence score (age_cor_score)

		and age-corrected list-sorting score (list_age_cor_scpre)
--	--	--

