## 9 Efficacy Analyses

For primary analyses for Protocol 1 Aims 1, primary outcomes will be compared between groups (heat therapy vs exercise training) over time (within subject repeated measurements) using two-way repeated measures mixed model including an interaction between intervention group and timepoint with pre-defined contrasts. For Specific Aim 1, to test the hypothesis that heat therapy improves blood pressure (both in clinic and 24H ambulatory) better than dynamic aerobic exercise, the null hypothesis will be that the interaction between group and timepoint is equal to 0. For Aim 2, to determine whether heat therapy will improve biomarkers of arterial health (arterial stiffness & biomarkers of systemic

inflammation and oxidative stress) and compare responses to exercise training, the null hypothesis will be that the interaction between intervention group and timepoint is equal to 0. For Aims 1 and 2 exploratory analyses, ANCOVA will be performed for primary and secondary outcomes, with pretest values entered as a covariate and treatment condition specified as a fixed factor. Demographic and physiological variables (age, sex, BMI) and pre-intervention blood pressure will be added one at a time to the ANCOVAs to test for an interaction on treatment effects. For Aim 3, we will use ANCOVA models to determine the predictive potential of acute post-exercise hypotension response for chronic changes in blood pressure, with pretest values entered as a covariate and systolic and diastolic blood pressure specified as a fixed factor. Analyses will be performed on the Intention to Treat population. Additionally, change from pre- to post-intervention in ambulatory and in clinic systolic and diastolic pressure will be correlated with change from pre- to post first intervention session supine systolic and diastolic blood pressure by Pearson correlation.

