## 9.1 Exploratory Efficacy Analyses

In addition to Protocol 1 primary analyses, additional exploratory analysis will include analyses of covariance (ANCOVA) for each dependent variable of interest, in which pretest values will be entered as a covariate and treatment condition will be specified as a fixed factor in ANCOVA models. Demographic and physiological variables age, sex, and body mass index will be added one at a time to the ANCOVAs to test for an interaction on treatment effects using the following ANCOVA models with pre-intervention systolic or diastolic blood pressure (Pre SBP, Pre DBP) included as a continuous covariate. ANCOVA models based on the formula Interim or Post BP ~ Pre BP + <Interaction variable> + Intervention + <Interaction variable>\*Intervention and included the following terms in addition to Pre BP: Model 2, Pre BP\*Intervention; Model 3, Age + Age\*Intervention; Model 4, Sex + Sex\*Intervention interaction; Model 5, BMI + BMI\*Intervention interaction. SBP, DBP, age and body mass index (BMI) will all included in models as continuous variables with means estimated at selected values of interaction terms to illustrate how blood pressure measures did or did not vary by subgroup.

For Protocol 1 Aim 3, which is an exploratory aim, analyses of covariance (ANCOVA) models will be used to determine the predictive potential of acute responses for chronic changes in blood pressure. To test the association between acute decreases in blood pressure following an initial heat therapy session or exercise peak test and sustained reduction in resting blood pressures as measured by post-intervention ambulatory blood pressure, we will perform ANCOVA models with pre-session systolic or diastolic blood pressure (Pre-session SBP, Pre-session DBP) included as a continuous covariate. Pre-session BP is an average of three pre-session measurements and Post-session BP is lowest

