average of three consecutive readings taken every five minutes in the 55-110 minutes following the hour-long intervention. Group means for ambulatory blood pressure at the post-intervention timepoint will be estimated using the following formulas: Model 1, Post ambulatory BP ~ Pre-session BP + Intervention; Model 2, Post ambulatory BP ~ Pre-session BP + Intervention + Intervention\* Pre-session BP; Model 3, Post ambulatory BP ~ Pre-session BP + Intervention + Post-session BP + Intervention\* Post-session BP. BP measures will be included in models as continuous variables with means estimated at selected values of interaction terms to illustrate how blood pressure measures did or did not vary by subgroup. Additionally, exploratory correlations and PCA were performed among the following Project 1 variables: age, body mass index (BMI), HbA1c, total cholesterol (TC), Interleukin-6 (IL-6), C-reactive Protein (CRP), urine albumin to creatinine ratio (UACR), estimated glomerular filtration rate (eGFR), 24H ambulatory systolic and diastolic blood pressure (Amb. SBP, Amb. DBP), arterial stiffness measure pulse wave velocity (PWV), IPAQ long form continuous score MET-minutes/week (IPAQ), pre-first session resting SBP and DBP, maximum drop in supine SBP or DBP in the 55-110 minutes post-first heat or exercise session (Supine SBP or DBP drop), and total peripheral resistance (TPR), pulse wave velocity (PWV), renin, angiopoietin-2 (Ang2), endothelin-1 (Et1), and urine aldosterone.

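### The added Aim 3 Pearson correlations relate two raw BP changes without conditioning on baseline BP or arm, so they cannot show prediction beyond baseline

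*SAP*

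**What the plan says.** SAP 9 (Efficacy Analyses) states that "change from pre- to post-intervention in ambulatory and in clinic systolic and diastolic pressure will be correlated with change from pre- to post first" session "supine systolic and diastolic blood pressure by Pearson correlation". SAP 13 dates the addition to 05/22/24: "The SAP was updated to include correlations between pre- to post-intervention in ambulatory and in clinic systolic and diastolic pressure and change from pre". Neither place names a covariate, a partial correlation or an arm term.

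The acute variable is a raw difference. SAP Table 4 defines it, for systolic pressure, as "Change from average pre-session resting SBP to Supine.SBP.low".

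SAP 4.1 gives the purpose of Aim 3: "These findings would provide significant predictive information beyond baseline resting blood pressures". The aim is labelled exploratory there and in SAP 9.1. Table 1 nevertheless lists acute and chronic pressure reductions in the primary-outcome row for Aim 3. SAP 7.5 states that multiple comparisons are not controlled.

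The correlations are not the only Aim 3 analysis:

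- SAP 9 first describes ANCOVA models with pretest values as a covariate.
- SAP 9.1 specifies "ANCOVA models with pre-session systolic or diastolic blood pressure (Pre-session SBP, Pre-session DBP) included as a continuous covariate".
- The only printed formula that carries the acute response begins "Model 3, Post ambulatory BP ~ Pre-session BP + Intervention + Post-session BP" and adds an intervention-by-post-session interaction.
- SAP 7.3 lists pre-intervention 24-hour ambulatory BP among the covariates for SAP 9.1, but none of the three printed Aim 3 formulas contains it. None has clinic BP as the outcome.

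**The concern.** A zero-order correlation between two changes does not hold starting BP fixed. Suppose participants who start higher have a larger true fall after the first session and also a larger true fall over the programme. The two falls then correlate even if the acute response adds nothing once baseline is known. Aim 3 needs that second, conditional statement.

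Of the Aim 3 analyses written out in enough detail to run, the correlation is the only one that pairs the acute change with the chronic change directly, and the only one that uses clinic BP. A reader could take a positive r as showing that a large first-session fall identifies those who will benefit. That is the inference at risk. Nothing in the Aim 1 or Aim 2 comparisons depends on it.

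**Working it through.** The documents give no expected r, power or sample size for these correlations, so there is no stated figure to reproduce. What can be checked is the mechanism.

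**Inputs.** n = 40 is the number of completers the protocol says it needs (section C, projected effect sizes and statistical power). The test is two-sided at 0.05. All correlations, slopes and SDs below are assumptions.

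**1. Critical value.** With 38 df, |r| must exceed 0.312.

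**2. One perfectly measured baseline.** If the acute and chronic falls correlate with baseline at ρ₁ and ρ₂ and are otherwise unlinked, induced r = ρ₁ × ρ₂. With ρ₁ = ρ₂ = ρ (simulated rejection rates, 4,000 runs each):

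| ρ | induced r | raw Pearson rejects | partial correlation given baseline rejects |
|---|---|---|---|
| 0 | 0 | 4.9% | 4.8% |
| 0.3 | 0.09 | 8.3% | 4.5% |
| 0.4 | 0.16 | 17% | 5.2% |
| 0.5 | 0.25 | 34% | 5.2% |
| 0.6 | 0.36 | 63% | 4.8% |

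The Fisher z approximation gives 8.5% at ρ = 0.3 and otherwise agrees with the simulation to within a point.

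**3. Separate, error-prone baselines.** This is nearer to the plan, because the ambulatory or clinic pre value and the pre-session supine value are different readings. Assumptions in mmHg:

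- True BP has SD 8.
- Reading error is 4 (ambulatory or clinic) or 5 (supine).
- Residual SD of the true change is 4.5 (chronic) or 5 (acute).
- Both true falls depend on true baseline with slope s, and there is no other link.

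Then cov = 64s², var(chronic change) = 64s² + 4.5² + 4² + 4² = 64s² + 52.25, and var(acute change) = 64s² + 5² + 5² + 5² = 64s² + 75. At s = 0.5, r = 16/√(68.25 × 91) = 0.20. At s = 0, r = 0: independent reading error alone induces nothing.

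Rejection rates from 3,000 runs per row, with arm terms left out. The middle column adjusts for both measured baselines. The last adjusts for pre-session BP only, as the printed Model 3 does:

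| s | raw Pearson | both baselines | pre-session only |
|---|---|---|---|
| 0 | 4.8% | 17% | 45% |
| 0.2 | 6.3% | 11% | 26% |
| 0.3 | 8.3% | 7.9% | 17% |
| 0.4 | 14% | 6.4% | 12% |
| 0.5 | 24% | 5.8% | 8.9% |

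**4. Reading the second table.** An error-prone baseline leaves part of true BP unexplained, and the post-intervention and post-session readings both still carry it. Given both measured baselines, the remaining variance of true BP is 1/(1/64 + 1/16 + 1/25) = 8.5. At s = 0 this gives a partial r of 8.5/√((8.5 + 36.25)(8.5 + 50)) = 0.17, where 36.25 = 4.5² + 4² and 50 = 5² + 5². Given pre-session BP alone, the remaining variance is 1/(1/64 + 1/25) = 18.0 and the partial r is 18.0/√((18.0 + 36.25)(18.0 + 50)) = 0.30.

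In this scenario, then, adding the pre-intervention value of the outcome improves on the printed Model 3 at every slope. It improves on the raw correlation clearly at slopes of 0.4 and 0.5, is about level at 0.3, and rejects more often than the raw correlation at 0 and 0.2.

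**The case against.** **Aim 3 already has a baseline-adjusted analysis.** This stands. The ANCOVAs come first in SAP 9, and the correlations are introduced as an addition. A reader who saw only the correlations might infer that Aim 3 ignores baseline BP; SAP 9 and 9.1 contradict that. The general ANCOVA sentence in SAP 9 speaks of chronic changes with pretest values as a covariate and is not limited to ambulatory BP. What remains is that the formulas in SAP 9.1 use only post-intervention ambulatory BP and leave out its own pre-intervention value, despite SAP 7.3.

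**Regression to the mean.** A reader might also infer that reading error in the baseline creates the correlation. It does not, because the two changes start from different readings. Only a true dependence of both falls on starting BP does so.

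**The upper magnitudes are not representative.** This also stands. The 34% and 63% figures need one shared, perfectly measured baseline and strong correlations. Separate readings give at most 24% over the slopes tried.

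**The correlation is a legitimate description.** It is. Aim 3 is exploratory, the sentence about information beyond baseline is rationale and not the formal hypothesis, and SAP 15 lists no table or figure for these correlations. That limits the consequence to interpretation. It does not make the correlation an answer to the conditional question.

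**Adjustment is not a cure.** This is correct, as the second table shows, and the fix must say so.

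**Conclusion.** The point holds as a minor one. The Pearson correlations in SAP 9 condition on neither baseline BP nor arm, so a positive result cannot by itself support prediction beyond baseline. The printed ANCOVA formulas fill the gap only in part.

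The size is not derivable from the documents. Under an assumed 0.3 to 0.6 correlation of each fall with a single perfectly measured baseline, induced r is 0.09 to 0.36, with about 8% to 63% rejection at n = 40. With separate error-prone readings and slopes of 0 to 0.5, r is 0 to 0.20, with about 5% to 24% rejection. If either true fall is unrelated to starting BP, the baseline mechanism produces no bias in the raw correlation. The effect of leaving out arm was not quantified. Aims 1 and 2 are unaffected.

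**What to change.** In SAP 9, for clinic and ambulatory SBP and DBP, fit Post BP ~ Pre BP + Pre-session BP + Intervention + acute change. Name the acute-change coefficient, with its confidence interval, as the Aim 3 result. Keep the Pearson correlations and label them descriptive. A partial correlation on the two baselines alone is not the same analysis, because it leaves out arm.

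Add one sentence on the limit: both baselines are measured with error, so a non-zero coefficient may partly reflect usual BP level that the baseline readings missed.

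The cost is a short edit and one model per outcome, on variables already collected. At n = 40 the residual degrees of freedom fall from 38 for the Pearson test to 35 (three lost; two if only the baselines are added). The other price is the one in the second table: where the falls barely depend on starting BP, the adjusted test can reject more often than the raw one. That is why the two should be shown together, with the adjusted estimate read cautiously.

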## 14 References

## 15 Listing of Tables, Listings and Figures

Below is a list of tables and figures to be produced.

Protocol 1

Table 1. Study group characteristics at screening

Figure 1. Flow diagram of the Heat Therapy vs Exercise Training in Hypertension clinical trial

Figure 2. Ambulatory systolic and diastolic blood pressure of participants in heat therapy or exercise training intervention groups averaged over 24 hours or daytime or nighttime measurements alone across study timepoints.

Figure 3. Clinic systolic and diastolic blood pressure of participants in heat therapy or exercise training intervention groups at each study timepoint.

Table 2. Estimated effects of heat therapy compared to exercise training on 24H ambulatory and in clinic blood pressure measures across timepoints by mixed effect model

Supplementary Table 1. Estimated effects of heat therapy compared to exercise training on daytime and nighttime ambulatory blood pressure measures across timepoints by mixed effect model

Supplementary Figure 1. Estimates of ambulatory systolic and diastolic blood pressure of participants in heat therapy or exercise training groups averaged over 24 hours or daytime or nighttime measurements alone across study timepoints.

Supplementary Figure 2. Estimates of systolic and diastolic blood pressure of participants in heat therapy or exercise training groups at pre-, interim-, and post-intervention timepoints.

Supplementary Figure 3. Percent change in average ambulatory systolic blood pressure from day to night of participants in heat therapy or exercise training groups across study timepoints.

Supplementary Figure 4. Percent change in average ambulatory diastolic blood pressure from day to night of participants in heat therapy or exercise training groups across study timepoints.

Table 3. Systolic and diastolic blood pressure dipper status by group and timepoint

Figure 4. Clinic secondary outcomes of participants in heat therapy or exercise training intervention groups at each study timepoint.

Supplementary Table 2. Estimated effects of heat therapy compared to exercise training on secondary in clinic outcome measures across timepoints by mixed effect model

Figure 5. Arterial stiffness of participants in heat therapy or exercise training intervention groups at each study timepoint.

Table 3. Estimated effects of heat therapy compared to exercise training on pulse wave

velocity measure of arterial stiffness across timepoints by mixed effect model

Figure 6. Biomarkers of inflammation and oxidative stress in heat therapy or exercise training intervention groups at each study timepoint.

Supplementary Table 3. Estimated effects of heat therapy compared to exercise training on biomarkers of inflammation and oxidative stress across timepoints by mixed effect  
05/17/2024: Additional exploratory correlation and PCA analyses were added to the analysis plan with subsets of Project 1 and Project 2 variables.

## Protocol 2

Figure 7. Volume of hippocampus by region and estimated Total Intracranial Volume (eTIV) by intervention group at pre- and post-intervention.

Figure 8. Cognitive measures by heat therapy or exercise training intervention group.

Table 4. Cognitive and brain biomarker outcomes by group and timepoint

Table 5. Cognitive and brain biomarker outcome associations with blood pressure and arterial stiffness

Supplementary Figure 5. Correlations between cognitive measures and brain biomarkers of ADRD-risk

Supplementary Figure 6. Principal component analysis plot showing the multivariate variation among participants in terms of cognitive measures and brain biomarkers of ADRD risk

Supplementary Figure 7. Hierarchical clustering of cognitive measures and brain biomarkers of ADRD risk

